5.4.5 Nasal Lavage

Nasal lavage may be associated with some transient discomfort due to the <10 second breath hold and the feeling of fluid in the nares. A very rare potential complication of nasal lavage is acute bacterial sinusitis (sinus infection). The nasal lavage procedure is considered minimal risk, and is often referred to as a nasal wash or nasal irrigation. A variety of over-the-counter products (such as the neti-pot filled with a saline solution) have been widely available for home use to safely flush out nasal passages and alleviate both nasal congestion and even sinusitis symptoms.

The study clinician may use their discretion as to whether to administer a nasal decongestant prior to the nasal lavage. The nasal decongestant may be associated with temporary discomfort such as burning, stinging, sneezing, or an increase in nasal discharge.

5.4.6 Influenza Vaccine

As part of standard of care, the study clinician will recommend the participant obtain the current influenza vaccine. Minor side effects are soreness, redness or swelling at the injection site, low grade fever and aches. If these problems occur, they begin soon after vaccination and are mild and short-lived. Almost all people who receive influenza vaccine have no serious problems from it. On rare occasions, flu vaccination can cause serious problems, such as severe allergic reactions.

5.4.7 Questionnaires

There is a possibility that participants may find the questions too personal. Participants may refuse to answer any questions that make them feel uncomfortable.

5.5 Potential Benefits

The results of the skin testing will be provided to participants. Participants will receive relevant asthma education consistent with Guidelines for the Diagnosis and Management of Asthma (EPR 3) for patients with asthma, including handouts listing ways to avoid common allergy and asthma triggers. The national asthma guidelines have emphasized that exposure of patients who have asthma to allergens to which they are sensitive has been shown to increase asthma symptoms and precipitate asthma exacerbations. Guidelines for the Diagnosis and Management of Asthma (EPR 3) state that the clinician should evaluate the potential role of allergens, particularly indoor inhalant allergens via medical history and skin testing, and then assess the significance of positive tests in the context of the patient's medical history. Patients who have asthma at any level of severity should: (1) reduce, if possible, exposure to allergens to which the patient is sensitized and exposed; (2) know that effective allergen avoidance requires a comprehensive approach; and (3) be provided with relevant educational materials for control of environmental factors.

While the participant's asthma may or may not improve while in this study, participants may directly benefit from study participation by receiving study-based asthma assessments and care from an asthma specialist. The participants will receive close monitoring and direct management of asthma exacerbations on a 24/7 basis throughout the study. Participants with uncontrolled asthma at Screening will benefit by having additional visits to bring their asthma under control before Randomization. Participant families will receive contact numbers for the study site and a tailored asthma action plan and education. A supply of prednisone will be provided in concert with this management.

In the longer term, this study may promote the further development of cockroach SCIT for asthma and allergic rhinitis, which could be a major advance in the care of individuals with these conditions who are allergic to cockroach antigens.

6 Investigational Agent

6.1 Investigational Agent

Non-standardized glycerinated German cockroach (*Blattella germanica*) allergenic extract (50% glycerin) will be used as the investigational agent in Protocol ICAC-28. Commercially-labeled licensed product was

purchased by the IND Sponsor from the manufacturer - Stallergenes Greer (Lenoir, NC) and distributed to the clinical research sites by DAIT NIAID drug distributor (Eminent Services Corporation, Frederick, MD).

6.1.1 Formulation, Packaging, and Labeling

The active ingredient of the investigational product is a non-standardized allergen derived from the extraction and purification of proteins from German cockroach (*Blattella germanica*). The allergenic extract contains the aqueous extractable from allergenic source material in extracting solution containing 0.25% sodium chloride, 0.125% sodium bicarbonate, and 50% glycerol. Phenol (0.4%) is added after extraction as a preservative.

Non-standardized glycerinated German cockroach allergenic extract is approved in the United States for diagnostic skin testing and immunotherapy by subcutaneous injection (U.S. License 467). It has been used in humans for at least 35 years. The recommended storage conditions for the investigational agent are 2°C to 8°C. For this protocol, German cockroach extract will be stored at minus 20°C. Storage at minus 20°C is to decrease the rate of degradation of allergen (Bla g5) in the extract.

6.2 Placebo

The placebo product for SCIT in Protocol ICAC-28 is a commercially-labeled licensed product, sterile diluent for allergenic extract [glycerin (50%), sodium bicarbonate (0.091%), sodium chloride (0.166%) with water for injection (q.s.)]. The commercially-labeled licensed product was purchased by the IND Sponsor from the manufacturer – Allergy Laboratories (Oklahoma, OK) and distributed to the clinical research sites by DAIT NIAID drug distributor (Eminent Services Corporation, Frederick, MD).

6.2.1 Formulation, Packaging, and Labeling

The placebo for immunotherapy will consist of the same inactive ingredients as the non-standardized glycerinated German cockroach allergen extract. It is not colored and is in 8mL multi-dose vials.

6.3 Dosage, Preparation, and Administration

6.3.1 Subcutaneous Immunotherapy

Cockroach allergenic extract or placebo is prepared by the clinical site research pharmacist. Complete details of the dilutions can be found in the Pharmacy Manual: Investigational Product Preparation and Dispensing for Subcutaneous Immunotherapy (SCIT) for Protocol ICAC-28.

Participants will receive escalating doses of glycerinated German cockroach allergenic extract or placebo administered subcutaneously according to the dose escalation schedule (Section 8.7.1).

6.4 Drug Accountability

Under Title 21 of the Code of Federal Regulations (21CFR §312.62) the investigator will maintain adequate records of the disposition of the investigational agent, including the date and quantity of the drug received, to whom the drug was dispensed (participant-by-participant accounting), and a detailed accounting of any drug accidentally or deliberately destroyed.

Records for receipt, storage, use, and disposition will be maintained by the study site. The drug-dispensing log will be kept current for each participant. These logs will contain the identification of each participant and the date and quantity of drug dispensed.

All remaining unused investigational product will be returned to the IND sponsor (DAIT, NIAID) or sponsor's representative after study termination, or destroyed with the permission of the sponsor in accordance with applicable law and study site procedures.

All records regarding disposition of the investigational product will be available for inspection by the clinical trial monitor.

6.5 Assessment of Participant Compliance with Investigational Agent

As participants receive their injections in the clinic, compliance will be monitored by assessing the number of expected and completed injection visits.

6.6 Toxicity Prevention and Management

In the case of a reaction to the subcutaneous investigational agent, dosing will be altered according to Section 8.6.1 Dose Escalation and 8.6.2. Maintenance Visits.

6.7 Premature Discontinuation of Investigational Agent

Participants who are unable to reach the minimum maintenance dose by 40 weeks following the start of dose escalation will be unable to proceed to the maintenance period and will have their study therapy discontinued (see Section 11.2.1 Discontinuation of Study Therapy; see Appendix B Study Restrictions Due to COVID-19).

Study therapy may be prematurely discontinued for any participant for any of the reasons identified in Section 11.2.1 Discontinuation of Study Therapy. Study therapy may also be prematurely discontinued for any participant if the study clinician believes that the study treatment is no longer in the best interest of the participant. Participants whose therapy is prematurely discontinued will be followed when possible for the duration of the study and seen for all remaining visits except Injection Visits.

7 Other Medications

7.1 Concomitant Medications

7.1.1 Protocol-mandated

All participants will receive asthma step care according to the Guidelines for the Diagnosis and Management of Asthma.²⁸ Treatment will be supervised by a study clinician. The study clinician will prescribe initial appropriate concomitant asthma therapies (see Section 7.1.1.1) and will provide a written Asthma Action Plan for the participant at Screening, Randomization, and every two months thereafter (see Section 7.1.1.4). The regimen will then be adjusted as necessary at those visits throughout the duration of the trial based on the principles of the EPR-3 guidelines (see Table 7.1.1.2a, below).

The study clinician will prescribe the appropriate step controller therapy according to the participant's insurance/health maintenance organization guidelines. The preferred controller steps and alternate equivalent medications may be modified or updated based on changes in standard clinical practice, discontinuation of current medications, or the introduction of new medications. For the standardized treatment of asthma exacerbations, the clinical research staff will provide oral prednisone and written instructions for use.

All participants are required to have medical insurance that will cover, at least in part, the costs of their asthma medications. It is likely, however, that some participants may lose this coverage during the time that they are in the study. To maintain participant safety and avoid a loss of these participants to the study, Protocol ICAC-28 CRITICAL will fund the cost of these participants’ asthma medications during the remainder of the study or until the participant regains insurance coverage during the study. Medications will be prescribed in the same manner using the same algorithms as all insured participants. Each research site will develop plans to use local pharmacies in a cost efficient and timely manner. This design is in place to mimic the support typical insured participants receive, i.e. they receive a prescription and have to fill it at a pharmacy. To limit the time that Protocol ICAC-28 CRITICAL is required to fund the cost of asthma medications for a participant who has lost coverage, each research site will develop a plan for evaluation of insurance options and referral to appropriate support systems to obtain coverage for medication costs. In addition to addressing potential insurance from employers and governmental sources, this may include free clinics and support programs available through pharmaceutical firms.

The study clinician is allowed to prescribe treatment for rhinitis symptoms as clinically indicated. No specific rhinitis medications are recommended or required to be used. The choice is study clinician discretion.

7.1.1.1 Initial Regimen

At the Screening Visit, the study clinician will determine the appropriate asthma control regimen that will be prescribed for the participant. Along with the participant’s medical history and physical examination results, the medication regimen is determined by the participant’s symptoms, number of systemic corticosteroid bursts in the past 6 months, percent-predicted forced expiratory volume in 1 second (FEV₁), and current level of asthma controller therapy.

First, the study clinician will determine the highest “control level” of the participant’s morbidity across the 4 categories in Table 7.1.1.1a. For example, if the participant has 8 days with symptoms (control level 2), 1 night with symptoms (control level 1), is at 75% predicted FEV₁ (control level 3), and has 0 systemic steroid bursts, (control level 1), then the participant is at control level 3 because that is the highest of these 4 categories.

Table 7.1.1.1a Asthma Symptoms for Determining Run-in Asthma Medication Regimen

Control Level	Maximum of 1) # days with asthma symptoms/ two weeks and 2) # days with rescue albuterol or levalbuterol use/ two weeks*	Maximum of 1) # nights of sleep disruption due to asthma/ 2 weeks and 2) # nights use of albuterol or levalbuterol for awakening / 2 weeks*	FEV ₁ (% pred)**	Courses of systemic steroids in the last 6 months***
1	0-3 days	0-1 night	≥ 85	0
2	4-9 days	2 nights	80 - < 85	1
3	10-13 days	3-4 nights	70 - < 80	2

4	14 days	5-14 nights	< 70	>2

FEV₁ = forced expiratory volume in 1 second; pred = predicted * Determined from participant recall, based on the 2-week interval directly preceding the study visit. **Predicted references are provided in the Protocol ICAC-28 MOP. *** Defined as a prescription of a course of systemic steroids by a clinician or initiation of a course of systemic steroids by a participant to prevent a serious asthma outcome. If a participant initiates and completes a course of systemic steroids without clinician involvement, this course will be counted only if it meets the following dosage: the course for prednisone, prednisolone, or methylprednisolone will be 2 mg/kg/day as a single daily dose for 4 days with a maximum dose of 60 mg per day. The course for dexamethasone will be 0.3 to 0.6 mg/kg/day as a single daily dose for 2 days with a maximum dose of 16 mg per day. If a corticosteroid burst for the treatment of an asthma exacerbation is prescribed by a non-ICAC clinician, it will be counted regardless of dose.
				

Next, the study clinician will determine the current level of controller therapy that the participant is using. Table 7.1.1.1b shows the asthma regimens that will be used during the treatment phase of Protocol ICAC-28 CRITICAL. If the participant is currently on one of the therapies below, then the step level of that therapy will be noted. Otherwise, the study clinician must refer to the Protocol ICAC-28 MOP for equivalency tables for other asthma therapies. From the information in the Protocol ICAC-28 MOP, the study clinician will determine the corresponding step level of therapy that the participant is currently using. For example, if the participant is currently taking Flovent® Diskus® 250 mcg twice per day (bid), then he/she is receiving Step 3 therapy.

Table 7.1.1.1b Asthma Regimen by Step Level of Therapy

Step	Medication Equivalent*
0	No controller medication; albuterol or levalbuterol prn
1	fluticasone 50 mcg bid
2	fluticasone 100 mcg bid
3	fluticasone 250 mcg bid
4	fluticasone 250 mcg bid plus LABA
5	fluticasone 500 mcg bid plus LABA

bid = twice per day; LABA = long-acting beta agonist

*Equivalent medication covered by participant’s insurance formulary – see Protocol ICAC-28 MOP.

Based on the participant’s current control level (from Table 7.1.1.1a) and the participant’s current step level of therapy (from Table 7.1.1.1b and the Protocol ICAC-28 MOP), the study clinician will find the corresponding row in Table 7.1.1.1c below that includes both the current regimen and the current control level. The last column of that row gives the corresponding regimen as a step level, which refers back to Table 7.1.1.1b. The study clinician will prescribe this regimen.

Continuing the example from above, since the participant is taking Step 3 therapy and is at control level 3, the regimen assigned would be Step 4 (fluticasone 250 mcg bid with LABA).

Table 7.1.1.1c Algorithm for Prescribing Treatment Regimen at Screening

Current Regimen	Current Control Level	Regimen Assigned
Regimen equivalent to Step 0 (or 1-3 days/week of a regimen equivalent to Step 1)	Control level 1 Control level 2 Control level 3 Control level 4	Step 0 Step 1 Step 1 Step 2 (and may also need prednisone burst)
Regimen equivalent to Step 1 (or 1-3 days/week of a regimen equivalent to Step 2)	Control level 1 Control level 2 Control level 3 Control level 4	Step 1 Step 2 Step 2 Step 3 (and may also need prednisone burst)
Regimen equivalent to Step 2 (or 1-3 days/week of a regimen equivalent to Step 3)	Control level 1 Control level 2 Control level 3 Control level 4	Step 2 Step 3 Step 3 Step 4 (and may also need prednisone burst)
Regimen equivalent to Step 3 (or 1-3 days/week of a regimen equivalent to Step 4)	Control level 1 Control level 2 Control level 3 Control level 4	Step 3 Step 4 Step 4 Step 5 (and may also need prednisone burst)
Regimen equivalent to Step 4 (or 1-3 days/week of a regimen equivalent to Step 5)	Control level 1 Control level 2 Control level 3 Control level 4	Step 4 Step 5 Step 5 Step 5 (and may also need prednisone burst)
Regimen equivalent to Step 5	Control level 1 Control level 2 Control level 3 Control level 4	Step 5 Step 5 Step 5 (and may also need prednisone burst) Step 5 (and may also need prednisone burst)

Note: Shading in the table corresponds to the example described in the text.

In addition to the controller regimen assigned above, all participants will be prescribed albuterol by metered-dose inhaler beta-agonist or nebulizer (per clinician discretion) to be used as needed and will be provided oral prednisone to be used as per protocol – see Section 7.4.1 and the Protocol ICAC-28 MOP. The study clinician will prescribe enough medication to last until the next E&M visit. If a participant is not eligible to continue, the study clinician may prescribe an appropriate treatment regimen based on clinical judgment.

7.1.1.2 Study Period Treatment Regimen

At Randomization and every 2 months during treatment, an asthma Evaluation and Management (E&M) process will occur where participants’ asthma medication regimen will be adjusted based on symptoms, albuterol/levalbuterol use, FEV₁, recent exacerbations, and their current level of therapy.

Participants may be stepped down from controller medications if their control level is equal to 1 at Screening, Asthma Control Visits, and at some E&M visits while the participant is in maintenance (see Appendix B: Study Restrictions Due to COVID-19). Participants may not be stepped down from controller

medications at Randomization or during Dose Escalation. Participants may be stepped up as per the protocol algorithm at any visit where indicated.

Participants will undergo pre-bronchodilator spirometry and an assessment of symptoms, rescue bronchodilator usage, recent exacerbations and medication adherence. Bronchodilator use as a preventive measure prior to exercise will not count toward the assessment of rescue bronchodilator use. Based on these data, a study clinician will determine the participant’s current control level from Table 7.1.1.2a below. The control levels originated from the published national guidelines, Guidelines for the Diagnosis and Management of Asthma.²⁸

For all participants, the highest control level for days with symptoms or albuterol/levalbuterol use, nights with symptoms or albuterol/levalbuterol use, percent personal best FEV₁, and exacerbation history will be determined by the study clinician. The day and night symptoms, albuterol/levalbuterol use, adherence to prescribed asthma controller medications by self-report, and exacerbation history will be determined from questionnaires. The FEV₁ personal best is defined in the Protocol ICAC-28 MOP. If the quality of the spirometry maneuver at the current visit is unacceptable according to the technician’s judgment, FEV₁ in Table 7.1.1.2a will not be used, and the control level will be based on day and night symptoms, albuterol/levalbuterol use, and exacerbation history. For example, if a participant has 0 days with symptoms (control level 1), 4 nights with symptoms (control level 3), FEV₁ at 85% of personal best (control level 1), and 1 exacerbation (control level 2), then the participant’s overall control level is 3 because that is the maximum value of control levels 1, 3, 1, and 2.

Table 7.1.1.2a Control Levels of Symptoms, Bronchodilator Usage, FEV₁ (% personal best), and Exacerbations

Control Level	Maximum of 1) # days with asthma symptoms/ 2 weeks and 2) # days with rescue albuterol/levalbuterol use/ 2 weeks*	Maximum of 1) # nights of sleep disruption due to asthma/ 2 weeks and 2) # nights use of albuterol/levalbuterol for awakening/ 2 weeks*	FEV ₁ (% personal best)	Courses of Systemic Steroids since the Last Medication Management Visit**
1	0-3 days	0-1 night	≥ 85	0
2	4-9 days	2 nights	80-84	1
3	10-13 days	3-4 nights	70-79	-
4	14 days	5-14 nights	< 70	-

FEV₁ = forced expiratory volume in 1 second

* Determined from participant recall, based on the 2-week interval directly preceding the study visit.

**Defined as a prescription of a course of systemic steroids by a clinician or initiation of a course of systemic steroids by a participant to prevent a serious asthma outcome. If a participant initiates and completes a course of systemic steroids without clinician involvement, this course will be counted only if it meets the following dosage: the course for prednisone, prednisolone, or methylprednisolone will be 2 mg/kg/day as a single daily dose for 4 days with a maximum dose of 60 mg per day. The course for dexamethasone will be 0.3 to 0.6 mg/kg/day as a single daily dose for 2 days with a maximum dose of 16 mg per day. If a corticosteroid burst for the treatment of an asthma exacerbation is prescribed by a non-ICAC clinician, it will be counted regardless of dose.

Note: Shading in the table corresponds to the example described in the text above.

Based on the overall control level and the participant’s estimated level of adherence, the study clinician will use Table 7.1.1.2b below to determine how the participant’s current therapy should be modified. At E&M Visits, the participant will be considered to have acceptable adherence if he/she reports having taken 50% or more of the prescribed doses in the last 2 weeks. Participants with unacceptable adherence will not be stepped up in the same way as those with acceptable adherence. Continuing with the same example, since this participant is at control level 3 and assuming he/she has acceptable adherence, the study clinician would recommend a 2-step increase in therapy (or an increase to Step 5 if on Step 4 or maintenance on Step 5 if already on Step 5). In all cases, consideration will be given to a burst of prednisone according to the suggestions in the table.

Table 7.1.1.2b Treatment Adjustment Based on Control Levels and Adherence

Control Level	Treatment Algorithm for Participants with Unacceptable Adherence	Treatment Algorithm for Participants with Acceptable Adherence
1	If on Step 0, maintain at Step 0 If on Steps 1-5, decrease controller regimen by 1 step ** Do not decrease controller regimen at Randomization or during Dose Escalation	If on Step 0, maintain at Step 0 If on Steps 1-5, decrease controller regimen by 1 step ** Do not decrease controller regimen at Randomization or during Dose Escalation
2	Continue same controller regimen or place on Step 2 therapy, whichever is higher	Increase controller regimen by 1 step, or continue Step 5 therapy if already on Step 5
3	Continue same controller regimen or place on Step 2 therapy, whichever is higher	No systemic steroids since the Last Medication Management visit* If on Steps 0-4 increase controller regimen by 1 step If on Step 5 continue Step 5 or treat with Step 5 and a 4 day burst of prednisone or equivalent; ≥1 course(s) of systemic steroids since the last E&M visit* If on steps 0-3 increase controller regimen by 2 steps If on treatment Step 4 increase controller regimen to Step 5 or treat with Step 5 and a 4 day burst of prednisone or equivalent If on treatment Step 5 continue Step 5 or treat with Step 5 and a 4 day burst of prednisone or equivalent
4	Continue same controller regimen or place on Step 3 therapy, whichever is higher OR Treat with 4-day prednisone burst and continue same controller regimen or place on Step 3 therapy, whichever is higher	If on Steps 0-3 increase controller regimen by 2 steps If on Step 4, increase to Step 5 or treat with Step 5 and a 4-day prednisone burst or equivalent If already on Step 5, continue on Step 5 or treat with Step 5 and a 4-day burst of prednisone or equivalent

*Defined as a prescription of a course of systemic steroids by a clinician or initiation of a course of systemic steroids by a participant to prevent a serious asthma outcome. If a participant initiates and completes a course of systemic steroids without clinician involvement, this course will be counted only if it meets the following dosage: the course for prednisone, prednisolone, or methylprednisolone will be 2 mg/kg/day as a single daily dose for 4 days with a maximum dose of 60 mg per day. The course for dexamethasone will be 0.3 to 0.6 mg/kg/day as a single daily dose for 2 days with a maximum dose of 16 mg per day. Note: Shading in the table corresponds to the example described in the text above.
		

Based on the participant's step level assigned at the last E&M visit and the change in steps determined above, the new regimen will be prescribed according to Table 7.1.1.2b above. In the example above, if the participant were currently on Step 2 and having no problems with adherence, then the recommended new treatment step based on symptoms, albuterol/levalbuterol use, FEV₁, and exacerbations is Step 4.

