4.2 Inclusion Criteria

Individuals who meet all of the following criteria are eligible for enrollment as study participants:

1. Subject and/or parent guardian must be able to understand and provide informed consent.
2. Are male or female children, 8 through 17 years of age at recruitment.
3. Have a primary place of residence in one of the pre-selected recruitment census tracts as outlined in the Protocol ICAC-28 Manual of Operations (MOP).
 - a. Participants who do not live in the pre-selected census tracts but live within the Office of Management and Budget (OMB) defined Metropolitan Statistical Area and have publicly-funded health insurance will qualify for inclusion.
4. Have a history of persistent asthma, for a minimum of 1 year before study entry.
 - a. A diagnosis of asthma will be defined as a report by the caretaker that the participant had a clinical diagnosis of asthma made by a clinician ≥ 1 year ago, resulting in a prescription of preventative asthma medication.
 - b. The participant must have persistent asthma defined by the current need for at least 88 mcg fluticasone (or the equivalent of another inhaled corticosteroid) to control asthma at the time of screening.
5. Before randomization, the participant's asthma must be well-controlled as defined by:
 - a. A FEV₁ greater than or equal to 80% predicted
 - b. An Asthma Control Test (ACT) or Childhood Asthma Control Test (CACT) score ≥ 20 .
6. Are sensitive to German cockroach as documented by a positive (≥ 3 mm greater than negative control) skin prick test result and detectable German cockroach-specific IgE (≥ 0.35 kU_A/L).
7. Have no known contraindications to therapy with glycerinated German cockroach allergenic extract or placebo.
8. Have a positive cockroach Nasal Allergen Challenge (NAC), as defined by reaching a Total Nasal Symptom Score (TNSS) of ≥ 6 or a sneezing score of 3 at dose 2 or above during the challenge before randomization.
9. Have documentation of current medical insurance with prescription coverage at randomization.

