The study clinician will assign the participant to the appropriate asthma treatment step based on the participant's current asthma medications and symptoms according to the treatment algorithm (see Section 7.1.1.1), write an appropriate prescription, and provide an asthma action plan (see Section 7.1.1.4). Participants will receive basic asthma education (see Section 7.1.1.5).

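### At Screening, Protocol Section 7.1.1.2 allows a controller step-down at control level 1, but the table assigned to that visit keeps every classified step unchanged, so regimens can differ by one step

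*Protocol*

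**What the plan says.** **Permission.** Protocol Section 7.1.1.2 (Study Period Treatment Regimen) says: "Participants may be stepped down from controller medications if their control level is equal to 1 at Screening, Asthma Control Visits". The sentence goes on to some E&M visits in maintenance. The next sentence bars step-down at Randomization and during Dose Escalation, and step-up is open at any visit where it is indicated. Table 7.1.1.2b gives the size of the decrease at control level 1: one step from Steps 1 to 5, with the same two exceptions.

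**Rule assigned to the visit.** Section 8.4.1 has the clinician set the step at the Screening Visit from current medication and "symptoms according to the treatment algorithm (see Section 7.1.1.1"). That section holds "Table 7.1.1.1c Algorithm for Prescribing Treatment Regimen at Screening", and of the step read from the table it says: "The study clinician will prescribe this regimen". The assigned steps run in order of control level 1 to 4. The Step 1 row reads "Step 1 Step 2 Step 2 Step 3 (and may also need prednisone burst") and the Step 3 row reads "Step 3 Step 4 Step 4 Step 5 (and may also need prednisone burst"). The first entry, for control level 1, is the current step.

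**Asthma Control Visits.** Section 8.4.3 says only that medication is adjusted where indicated. It names no table.

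**Analysis.** Asthma treatment step is exploratory endpoint 2e (Protocol Section 3.4). Protocol Section 13.4.5.3 and SAP Section 8.4.3 analyse it with the CASI mixed model and that model's covariates, which are treatment group, site and baseline CASI.

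**The concern.** Two passages speak to the same visit and the same child and give different regimens. One prescribes the current step and contains no decrease. The other lists that visit among those where a decrease is allowed. The word *may* does not reconcile them, because using the permission means departing from a regimen that the clinician is told to prescribe. Section 7.1.1.1 opens the way to clinical judgment only for a child who is not eligible to continue.

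At stake are the controller regimen that a child carries into the trial, possibly eligibility at the upper end of the dose range, and the starting point for the exploratory asthma outcomes.

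**Working it through.** The plan states no figure to reproduce, so the check sets the tables side by side at control level 1. Daily doses are the twice-daily doses of Table 7.1.1.1b multiplied by two. Section 7.1.1.2 does not give the size of the Screening step-down, so I assume the one step of Table 7.1.1.2b.

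| Classified step at Screening | Fluticasone per day | Step under Table 7.1.1.1c | Step if 7.1.1.2 permission is used | Gap |
|---|---|---|---|---|
| 0 | none | 0 | 0 | 0 |
| 1 | 2 × 50 = 100 mcg | 1 | 0 | 1 |
| 2 | 2 × 100 = 200 mcg | 2 | 1 | 1 |
| 3 | 2 × 250 = 500 mcg | 3 | 2 | 1 |
| 4 | 2 × 250 = 500 mcg + LABA | 4 | 3 | 1 |
| 5 | 2 × 500 = 1000 mcg + LABA | 5 | 4 | 1 |

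Table 7.1.1.1c leaves 6 of 6 rows unchanged at control level 1. The permission, where used, lowers 5 of 6.

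**Partial use.** The rows also classify irregular users, for example "Regimen equivalent to Step 3 (or 1-3 days/week of a regimen equivalent to Step 4"). A child who takes Step 4 on 1 to 3 days a week is classed as Step 3 and, at control level 1, is assigned Step 3. The nominal prescription can therefore fall under the table. This depends on irregular use and is not the general step-down that Section 7.1.1.2 describes.

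**Persistence.** A child with FEV1 of at least 80% predicted and an ACT/CACT score of at least 20, who meets the other criteria, can go on to Randomization without an Asthma Control Visit. Step-down is then barred at Randomization and throughout escalation, which Appendix A puts at 16 to 26 weeks normally and up to 40. A one-step gap set at Screening can last that long unless a step-up closes it.

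**Exclusion 4a.** This excludes, at the time of randomization, a child who requires more than 500 mcg of fluticasone a day. If the required dose is read as the dose prescribed, a Step 5 child at control level 1 stays at 1000 mcg under Table 7.1.1.1c, above the limit. With the permission used, the child is at 500 mcg, which is not above it. The criterion does not say how the required dose is established, so this effect is possible rather than certain.

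**Reach into the analysis.** The choice is made before allocation and cannot depend on arm. Randomization is stratified by site, and the exploratory asthma models include site, so average differences between sites are adjusted for. Differences within a site in starting step are not, because the treatment-step model as written carries over baseline CASI and not baseline step. The primary model (SAP Section 8.2.2) contains treatment, baseline mean TNSS and site only.

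**The case against.** The strongest reply is that the documents already show which rule operates. Section 8.4.1 points to Section 7.1.1.1, whose wording is mandatory. The permission sits in a section about the study period. The Manual of Operations, which is not available here, may settle the matter. This makes it plausible that sites simply used Table 7.1.1.1c, and nothing shows that they split. It does not remove the contradiction, because Section 7.1.1.2 names Screening expressly.

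A second reply also stands in part. SAP Section 6.2 already defines baseline as the last measurement before or on the day of randomization. That fixes the timing of a baseline value but does not put baseline step into the model.

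A reader might infer more than the text supports:

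- *A contradiction at Asthma Control Visits.* Table 7.1.1.1c is titled for Screening only. Section 8.4.3 is compatible with Section 7.1.1.2 and Table 7.1.1.2b. The defect there is that no algorithm is named.
- *A conflict with inclusion 4b when Step 1 falls to Step 0.* That criterion asks for a "current need for at least 88 mcg fluticasone" at the time of screening. A Step 1 child, at 100 mcg a day, meets it on entry, and it does not say what must be prescribed afterwards.
- *Many children affected.* No count is given. Control level 1 is also stricter than eligibility on lung function: FEV1 of at least 85% predicted against 80%. It further requires no systemic steroid course in six months, at most 3 symptom or rescue days and at most 1 night in two weeks.
- *A floor effect in the treatment-step outcome.* The documents give no distribution of steps from which to show one.
- *A link to fatal reactions through unstable asthma (Section 5.2).* Step-down requires control level 1, and control is checked again before the challenge (8.1.5), at randomization (8.5) and before each injection (8.1.2, 8.6.1).

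**Conclusion.** The contradiction at Screening is real and can be checked from the text. It amounts to one step for a child on Steps 1 to 5 at control level 1, assuming the decrease in Table 7.1.1.2b applies. How many children this concerns, and which passage sites followed, cannot be known from the documents.

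It should not be read as a threat to the trial's main result: it does not bias the comparison of arms and does not enter the primary TNSS analysis. What remains is extra variation in baseline asthma step and in CASI for exploratory endpoints, and a possible effect on exclusion 4a for a Step 5 child. Severity is minor.

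**What to change.** 1. Reconcile Protocol Section 7.1.1.2, Table 7.1.1.1c, Table 7.1.1.2b and Sections 8.4.1 and 8.4.3 so that one rule applies at control level 1 at Screening. Name the algorithm used at Asthma Control Visits. Which clinical rule should apply is for the sponsor to decide, and this review takes no view.
2. In the exploratory treatment-step model (Protocol Section 13.4.5.3, SAP Section 8.4.3), use the step in force at randomization as the baseline covariate. State whether that is the step before or after the adjustment made at the Randomization Visit.

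The cost is protocol wording, a site memo and one line in the SAP, with no new visits or data. The SAP describes randomization in the past tense, so a memo may come too late to change prescribing. In that case, record which rule sites followed at Screening and keep the second change.
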